# 4.5.3.2 Secondary endpoints

# 4.5.3.2.1 Pediatric Daytime Sleepiness Scale scores (PDSS)

PDSS is a sum score with 8 items leading to a score range of 0-32. A score greater than 13 is considered as abnormal sleepiness.

## Analysis:

The difference between placebo and BF2.649 will be studied in the same way as the primary analysis (Including sensitivity analyses).

In addition,

- Descriptive statistics at baseline and at each post-baseline visit by treatment group and an évolution graph of Mean ± SE will be provided.
- Comparison by treatment group of the response to the treatment (between Baseline value and End of treatment value) using a Chi2 test will be provided.

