#### 4.1.4 Missing data

#### 4.1.4.1 General considerations

(ICH E3; 9.7.1, 11.4.2.2. ICH E9; 5.3. EMA Guideline on Missing Data in Confirmatory Clinical Trials) Missing data will be imputed for five main endpoints of this study (UNS, PDSS, UNS-CTP, WRC and MWT). For the other endpoints no missing value will be imputed.

A Multiple Imputation (MI) procedure will be used to impute the missing evaluations, as a prior step, assuming that those patients would be in their randomized arm. The partially complete datasets will be generated with a model including the following covariates age, gender and the main model components (section 2.2).

A total of 100 imputed partially complete datasets will be generated.

MI inference involves 3 consecutives phases:

- 1/ Imputation step:

The missing pattern is supposed to be monotone, so the regression method will be used to impute missing data.

The partially complete datasets will be generated with a model including age, gender factors and taking into account the baseline score of the primary endpoint, based on patient which every postbaseline measurement available. It is of note that this imputation step might be preceded by one MI approach based on MCMC method, in case of arbitrary missing pattern. A total of 100 imputed partially-complete datasets will be generated.

The mean MD imputation will based on Missing at Random (MAR) corresponding to the hypothesis that missingness is assumed independent of the outcome, or to estimate a "de jure" (per protocol) estimand, censoring after any protocol deviation. This hypothesis was considered as the most likely in this particular context.

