# Pediatric Daytime Sleepiness Scale scores (PDSS)

The response to treatment according to PDSS is derived at a visit as a score reduction of 3 Between the baseline and the final value:

- If  $PDSS_B-PDSS_F \ge 3$  then response to treatment at the visit = Yes.
- If PDSSB-PDSSF < 3 then response to treatment at the visit = No.
- Otherwise, response to treatment at the current visit is not calculated.

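### The supportive PDSS responder comparison leaves out baseline PDSS, which costs roughly 2 to 7 power points, and the SAP does not say how a missing response is handled

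*SAP*

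**What the plan says.** PDSS is the first secondary endpoint in the fixed sequence of SAP 4.1.3.2. Under SAP 4.5.3.2.1 the score "will be studied in the same way as the primary analysis (Including sensitivity analyses"), that is, by multiple imputation followed by the general model of SAP 4.1.3.1, which has baseline as a fixed covariate and centre as a random intercept. The same section then adds that a between-group comparison of response, from baseline to end of treatment, "using a Chi2 test will be provided".

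SAP 4.1.5.5 defines response as "derived at a visit as a score reduction of 3" points or more from baseline to final value. If the difference is not available, the rule is: "Otherwise, response to treatment at the current visit is not calculated".

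On missing data, SAP 4.1.4.1 states: "Missing data will be imputed for five main endpoints of this study (UNS, PDSS, UNS-CTP, WRC and MWT"). It continues: "For the other endpoints no missing value will be imputed". The responder variable is not named on either side of that line.

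The list of statistical elements for PDSS contains only a difference in adjusted means with its CI and p-value. No effect measure is specified for the responder comparison.

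**The concern.** There are two separate gaps.

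**Baseline.** Response is a threshold on a change score, so it depends on where the child started. A test that ignores baseline discards information already collected. SAP 4.1.3.1 allows departures from the general model where they are specified, so naming a chi-square test contradicts nothing. But no reason is given for dropping the covariate here.

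**Missing response.** The PDSS score is imputed. Whether responder status is then derived from the imputed scores is not stated. If it is not, the mean difference and the responder difference for the same endpoint describe different sets of children under different missing-data assumptions. If it is, the plan is still incomplete: SAP 4.1.4.1 pools an estimate and its variance by Rubin's formulae, and a chi-square test with no named estimate supplies neither.

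At stake is the clarity and efficiency of a supportive result, not the trial's conclusion.

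**Working it through.** **1. The plan's own figures.** The documents give no power, response rate or PDSS SD for the responder comparison, so there is no direct figure to reproduce. The only PDSS power statement (SAP 4.2: 20 + 40 patients, standardised difference 0.5, R = 0.5, power 0.8) does reproduce with two pre- and two post-measures:
- residual variance = (1 + R)/2 − 2R²/(1 + R) = 0.75 − 0.333 = 0.417, so SD = 0.6455
- power = Φ(0.5 / [0.6455 × √(1/20 + 1/40)] − 1.96) = Φ(0.87) ≈ 0.81

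The current statement of 0.85 at 36 + 72 concerns UNS and is not used here beyond the group sizes and R.

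**2. Does baseline predict response?** With equal SDs at baseline and final, the correlation between baseline and the reduction is √((1 − R)/2):
- R = 0.4 (SAP 4.2, for UNS): √0.30 = 0.55
- R = 0.5 (SAP 4.2, for PDSS): √0.25 = 0.50

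The entry cut-off of PDSS ≥ 15 (Protocol 3.4.1) narrows the baseline range. It weakens this link but does not remove it.

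**3. Power of the candidate tests.** Inputs from the documents:
- 36 + 72 patients, two-sided 0.05 and a standardised difference of 0.5
- R of 0.4 or 0.5
- response = fall ≥ 3
- missing rate 2/27 = 7.4% (Protocol 7.7.2: 25 of 27 randomised patients gave values at V6 and V7)

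Assumptions not in the documents: normal scores, PDSS SD of 4, 5 or 6, mean placebo change −2, and data missing completely at random. The simulation used 1,000 trials per row. Imputation was from baseline and treatment, with 20 imputations instead of the SAP's 100.

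| SD | R | Response, placebo / pitolisant | Chi-square, observed | Chi-square, nothing missing | Logistic + baseline, observed | Imputed, logistic + baseline | Imputed, unadjusted difference |
|---|---|---|---|---|---|---|---|
| 4 | 0.4 | 41% / 59% | 0.409 | 0.439 | 0.460 | 0.459 | 0.429 |
| 4 | 0.5 | 40% / 60% | 0.475 | 0.479 | 0.534 | 0.529 | 0.485 |
| 5 | 0.4 | 43% / 61% | 0.403 | 0.429 | 0.470 | 0.464 | 0.418 |
| 5 | 0.5 | 42% / 62% | 0.443 | 0.458 | 0.492 | 0.490 | 0.450 |
| 6 | 0.4 | 44% / 62% | 0.421 | 0.445 | 0.460 | 0.460 | 0.448 |
| 6 | 0.5 | 43% / 63% | 0.482 | 0.496 | 0.535 | 0.535 | 0.495 |

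Reading across each row:
- Adding baseline gains 0.039 to 0.067, about 4 to 7 points.
- Imputation changes the adjusted test by −0.006 to 0, so it gains nothing.
- Imputation adds 0.007 to 0.027 to the unadjusted comparison, about 1 to 3 points.
- With 15% missing (SD 5, R 0.5), the chi-square test has 0.454 and the imputed adjusted test 0.478.
- With no true effect (SD 5, R 0.5), rejection rates are 0.057 (chi-square), 0.053 (adjusted) and 0.051 (imputed and adjusted). The adjustment does not inflate type I error.

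**4. With the entry cut-off.** Restricting baseline PDSS to 15 or more, over the same SD and R range, gives a gain of about 2 to 6 points. Over both sets of runs the chi-square test has power of about 0.40–0.52 and the adjusted test about 0.45–0.58, with a gain of 2 to 7 points.

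**5. Who would be left out?** Under SAP 4.1.5.1 a single value at V6 or V7 is enough for an End value. On an observed-case reading, only children with neither visit are lost. The 2 of 27 in Protocol 7.7.2 is the only guide to how many that might be.

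**The case against.** The strongest reply is that nothing confirmatory hangs on this. SAP 4.1.3.2 tests UNS, PDSS, UNS-CTP, WRC and MWT in order and treats everything else as exploratory and supportive. The responder comparison comes under additional analyses and carries no alpha. A chi-square test between randomised groups is valid, and it matches the SAP's responder analyses for CGI-C and patient's global opinion. All of that stands, and it limits the importance of the point. It does not explain why a covariate already in the general model is left out. Those two responder analyses also specify a difference in proportions with CI, which the PDSS one lacks, and SAP 4.5.3.2.3 already uses logistic regression with an odds ratio and 95% CI for WRC below 1.

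A reader might go further and infer that the SAP restricts this test to observed cases, and that losing the dropouts is what costs power. The documents do not support either step. No sentence says observed cases only. The SAP states non-imputation explicitly for UNS-EDS, CGI, CASS, TEA-Ch, the other diary measures and patient's global opinion, but not in the PDSS section, and PDSS is on the imputed list. The rule that response is not calculated would not apply if imputed scores fed it. Observed cases is the more natural reading of SAP 4.1.4.1 and 4.1.5.5, but it remains an inference. The power loss comes from the missing covariate; imputation recovers essentially none of it in the adjusted test.

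It is also fair to say that the SAP plans an observed-case analysis of mean PDSS among its sensitivity analyses. Even on the observed-case reading, a mean difference on matching patients would therefore be available.

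**Conclusion.** The point holds as a small, optional improvement. The responder test omits a useful covariate, at a cost of about 2 to 7 power points on a test whose power is only about 0.40–0.52. The handling of missing response is unstated and should be settled before unblinding. The figures rest on an assumed PDSS SD of 4 to 6, a placebo change of −2, a standardised difference of 0.5, R of 0.4 to 0.5 and 7.4% missing completely at random. The size of the gain moves with these; its direction did not change in any scenario run.

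The reason to derive response from the imputed scores is consistency with the main PDSS analysis, not power. The confirmatory PDSS result rests on the imputed, baseline-adjusted mean comparison and is unaffected.

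**What to change.** In SAP 4.5.3.2.1:
- Derive PDSS response in each of the 100 imputed datasets already planned for the score.
- Fit a logistic regression on treatment and baseline PDSS in each, with centre if it can be estimated. Pool the log odds ratios by Rubin's rules and report the odds ratio with 95% CI.
- Keep the chi-square test as supportive, add a difference in proportions with 95% CI, and state that it uses observed cases.
- Confirm that the imputation model for PDSS contains treatment and baseline PDSS. The imputation step reads "The partially complete datasets will be generated with a model including age, gender factors and taking into account the baseline score of the primary endpoint", which taken literally would be the UNS baseline, although the same section also refers to the components of the main model.

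The cost is a short SAP edit and a few lines of code, with no new data or patients. There are two minor drawbacks. The odds ratio is conditional on baseline and harder to read than a difference in proportions, which is why both should be shown. A centre term may not be estimable in about 108 patients, so the SAP should say that it is dropped in that case.

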## Statistical elements:

For this comparison the following elements will be provided in a summary table:

- Estimate (standard error) of the difference between adjusted treatment group means.
- Two-sided 95% CI of the estimate.
- p-value (to be compared to 0.05).

## 4.5.3.2.2 Ullanlinna Narcolepsy Scale Cataplexy subscore (UNS-CTP)

This subscore is defined as the sum Sum of the first four items of the UNS. (Cf. 7 Plazzi, G, P.Lehert, 2021)

## Analysis:

The difference between placebo and BF2.649 will be studied in the same way as the primary analysis (Including sensitivity analyses), only in the type I Narcolepy patients. In addition,

 Descriptive statistics at baseline and at each post-baseline visit by treatment group and an évolution graph of Mean ± SE will be provided.

- Descriptive statistics at baseline and at each post-baseline visit by treatment group of the response to the treatment will be provided.

## Statistical elements:

For this comparison the following elements will be provided in a summary table:

- Estimate (standard error) of the difference between adjusted treatment group means.
- Two-sided 95% CI of the estimate.
- p-value (to be compared to 0.05).

## 4.5.3.2.3 Weekly rate of Cataplexy (WRC)

Patients (or assisted by their parents or legal representative or teacher) shall fill in the document on a daily basis throughout the double blind phase (13 weeks) and the 7-day prior to the next visit during the open-label period. At each visit the patient should bring back his/her diary to the site for review by the investigator. The investigator reviewed these records with the patient.

One of calculated parameters is the Weekly rate of cataplexy (partial and total).

## Analysis:

A negative Binomial Regression will be used according to the general model (section 2.2) for WRC estimated during the period V6-V7 (Justification Plazzi 2021) only in the type I Narcolepy patients (for other patients we don't have the baseline value). The WRC at baseline will be used as a fixed covariate and center as random (In case of non convergence of the model, this one can be updated).

The same way as the primary analysis (Including sensitivity analyses) will be performed: MAR and MNAR imputation and observed cases.

In addition,

- Descriptive statistics by treatment group during the following intervals: Baseline (D-28 to D0),
   Final DB last 6 weeks DB4=D21-D63 (i.e. V4-V7), Final DB last 2 weeks: DB2=D49-D63 (i.e. V6-V7) will be provided
- A supportive analysis will be to compare the proportion of patients such that WRC <1 between treatment groups (simple logistic regression providing OR with 95%CI)

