3.3.2. Secondary endpoints

As secondary endpoints the study will assess efficacy and safety endpoints in pitolisant and placebo groups:

- Changes in EDS as measured by the maintenance of wakefulness test (MWT) between baseline and V7,
- Changes in EDS measured by the Paediatric Daytime Sleepiness Scale (PDSS) between baseline: [V1 score (D-14) + V2 score (D0)]/2 and the end of treatment: [V6 score (D49) + V7 score (D56)]/2,
- Changes in EDS as measured by the Child and Adolescent Sleepiness Scale (CASS) between baseline and the end of treatment.
- Changes in the average number of cataplexy episodes per weeks: (recorded in sleep diary by patient and/or parent/teacher) between the 2 weeks of baseline and the 2 weeks of end study treatment period (V6, V7),
- Differences in weekly frequency of cataplexy episodes (recorded in sleep diary by patient and/or parent/teacher) between baseline and the 4 weeks of stable treatment period (V4 to V7),
- Severity of EDS measured by the clinical Global Impression of severity and change. Changes between baseline and V6, V7,
- Severity of cataplexy measured by the clinical Global Impression of severity and change. Changes between baseline and V6, V7,
- Changes between baseline and V6 will be compared for the TEA-Ch test,
- Comparison between placebo and pitolisant groups on:
 - Withdrawal symptoms questionnaire (DSM IV) on D59 during a phone call (T1) and at the end-of-study visit on D63 (V8) after a one-week period on placebo,
 - Patients' Global Opinion on treatment effect at the end of treatment if able to express

Protocol P11-06/ BF2.649 EudraCT number: 2013-001506-29

himself. If not will be reported either by parents or teachers.

- ,Tolerability as measured by Treatment Emergent Adverse Events (TEAE),
- Changes in Physical examination and Vital signs,
- ECG and calculation of Fridericia's corrected QTc interval (QTcF = $QT/\sqrt{3}\sqrt{60/HR}$),
- Blood laboratory tests (haematology, blood chemistry),
- Mood appraisal adapted to children (CDI and C-SSRS).
- Changes between baseline and at each visit of the open-label period in EDS,
- Safety assessment will be done on monitoring of adverse events, physical examination, vital signs, ECG and Blood Laboratory tests modifications and the mood appraisal throughout the study.

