- 13) Active clinically significant illness, including unstable cardiovascular, endocrine, neoplastic, gastrointestinal, haematological, hepatic, immunologic, metabolic, neurological (other than narcolepsy/cataplexy), pulmonary, and/or renal disease which could interfere with the study conduct or counter-indicate the study treatments or place the patient at risk during the trial or compromise the study objectives.
- 14) Prior severe adverse reactions to CNS stimulants.
- 15) Known hypersensitivity to the tested treatment including active substance and excipients.
- 16) The inability to continue daily activities safely, without the use of treatment against EDS.
- 17) Any patient presenting congenital galactosemia, glucose-galactose malabsorption or lactase deficiency due to the presence of lactose in investigational treatments.
- 18) Patients participating in another study or being in a follow-up period for another study.
- 19) Cannot be contacted in case of emergency.

STUDY TREATMENT

Patients will be outpatients followed in ambulatory way during the whole study period and they will all receive the investigational study treatment pitolisant or placebo as described § 4.2. Patients will be asked to take the study drug every day before breakfast, according to the investigator's prescription regarding the dose regimen of patients, based on the product efficacy

and tolerance.

The total treatment duration of this double blind study is 8 weeks. Patients will start pitolisant treatment with escalating doses scheme on the first 4 weeks, as follows:

- V2 5 mg of BF2.649 or placebo / day during the first week,
 - 10 mg of BF2.649 or placebo /day during the second week,
- V3 Increase to 20 mg/d or maintain at 10 mg/d or reduce to 5 mg/d of BF2.649 (or placebo) per day for 7 days depending on efficacy and tolerability.

- V4 It will also be possible to reduce the dose administered to the patients, or to increase it without exceeding 40 mg/d. Patients with a weight less than 40kg could be treated with a maximum daily dose of 20mg.
- V5 It will be possible to reduce the dose administered to the patients, but not to increase it.
 - As from V5 onwards, no dosage change of the study treatment will be authorized.
- At the end of the double blind treatment (V7), the investigator will provide placebo to all patients for the one-week wash out period.

In open-label period patients will start pitolisant treatment with escalating doses scheme, as follows:

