3.7.1.2.6. Patient sleep diary

Patient sleep diary (Appendix 6) information from V1 (or from V0 when applicable) to V8 will be analyzed.

Patients (or assisted by their parents or legal representative or teacher) shall fill in the document on a daily basis throughout the double blind phase (13 weeks) and the 7-day prior to the next visit during the open-label period. During the first screening visit (V1 or from V0 when applicable), patients will be instructed on the daily use of diary by study investigators.

At each visit the patient should bring back his/her diary to the site for review by the investigator. The investigator should review these records with the patient.

In the active treatment group and in the placebo group, the score difference between the average number of cataplexy episodes (partial and total) per weeks between the 2 weeks of baseline and the 2 weeks of end study treatment period (V6, V7) and the differences in weekly frequency of cataplexy episodes between baseline and the 4 weeks of stable treatment period (V4 to V7).

In the open-label period, the difference between, the average number of cataplexy episodes

(partial and total) per weeks, the differences in weekly frequency of cataplexy episodes, between baseline and the 7-day prior all visits of the open-label period will be compared.

From the sleep diary, it will also be possible to check: Investigator should review the patients' and parents' estimate with them

- Hour of bedtime in the evening, wake-time in the morning.
- Number of diurnal involuntary sleep attacks and episodes of severe daytime sleepiness.
- Occurrence and number of cataplexy attacks (total or partial).
- Number of hallucinations and sleep paralysis.

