# 4.1.5.3 Completers

- Completers the double blind period Patients who completed the study until the visit V7.
- Completers the blind period Patients who completed the study until the visit V8.

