## Maintenance of Wakefulness Test 30-minute version

For this assessment the four test have been considered. Therefore, arithmetic means and sum on these 4 tests are computed.

**Mean value for each latency parameter**, in minutes, for a visit, will be estimated as the arithmetic mean of the 4 tests.

**Before this mean computation each latency parameter** (sleep onset, Stade I, Stade II, stade III and SP) must be recalculed to take into account the "Awake" status and the test duration:

- For a test, if "Awake"= "yes" then the sleep onset latency has to be considered at 30min (even if another value is entered).

- If a reported value is greater than 30min this value will be censured at 30min.

Number of Sleep onset in SP for a visit, will be computed as the sum of Yes (=1) of the 4 tests.

A survival response will be computed according to the "sleep onset latency" recalculed:

- Non-response (0=patient remained awake until 30 minutes) = Mean sleep onset latency ≥ 30min.
- Response (1=patient falling asleep before 30 minutes) = Mean sleep onset latency < 30min.

- Patient sleep diary
- Rate of cataplexy (WRC), Number of diurnal involuntary sleep attacks and episodes of severe daytime sleepiness (NSAE) and Number of hallucinations and sleep paralysis episodes (NHS) are weekly ratio computed as :

[Number of episodes of the concerned parameter in the period / Number of days in the period] \* 7

Whith Number of days in the period= Date of the last visit of the period - Date of the first visit of the period + 1

Results are rounded to to the nearest integer number.

- Night duration (NightD), in hours, is calculated as:

Wake-time (morning) - Hour of bedtime (evening)

The mean of night duration per day during the studied period is computed as:

Sum of night duration in the period / Number of days in the period

Whith Number of days in the period= Date of the last visit of the period - Date of the first visit of the period + 1

The result is rounded to one decimal place.

In case of several hours at the same date the following rule will be applied:

- For wake-time the last hour will be kept
- For bedtime the first hour will be kept

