#### Analysis:

Descriptive statistics by treatment group during the following intervals: Baseline (D-28 to D0), Final DB last 6 weeks DB4=D21-D63, Final DB last 2 weeks: DB2=D49-D63 will be provided

Missing data handling:

Missing evaluations are not imputated

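### The SAP's end-of-treatment diary windows contradict themselves: the day labels take in the all-placebo week, and no reading gives the protocol's two on-treatment weeks for the cataplexy rate

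*SAP*

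**What the plan says.** The SAP describes end-of-treatment diary data in three places.

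- SAP 4.5.3.2.3 (WRC) places the confirmatory negative binomial model on one window: "for WRC estimated during the period V6-V7". The descriptive bullet that follows gives "Final DB last 6 weeks DB4=D21-D63 (i.e. V4-V7), Final DB last 2 weeks: DB2=D49-D63 (i.e. V6-V7) will be provided".
- SAP 4.5.3.3.6 (other diary variables: night duration, sleep attacks, hallucinations and sleep paralysis) gives the day labels alone: "Final DB last 6 weeks DB4=D21-D63, Final DB last 2 weeks: DB2=D49-D63 will be provided".
- SAP 4.1.5.5 computes each weekly rate as episodes divided by days in the period, times 7, with the number of days equal to "Date of the last visit of the period - Date of the first visit of the period + 1".

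On where treatment ends, the documents agree. Protocol 5.2.8 puts V7 at D56 and 5.2.10 puts V8 at D63, each ±2 days. The Study Treatment section of the protocol says "At the end of the double blind treatment (V7), the investigator will provide placebo to all patients for the one-week wash out period". SAP 4.1.5.3 also closes the period at V7: "Completers the double blind period Patients who completed the study until the visit V7".

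Protocol 3.3.2 sets the cataplexy endpoint over "the 2 weeks of end study treatment period (V6, V7"). A second endpoint, described again in 3.7.1.2.6, covers "the 4 weeks of stable treatment period (V4 to V7"). Protocol 5.1 and SAP 3.3.1 place the four-week stable phase at V5 to V7. SAP 4.6 reports no modifications from the protocol's statistical section.

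**The concern.** A window ending at D63 cannot be V6-V7 or V4-V7, because V7 is D56. The extra week is one in which the pitolisant arm is on placebo. If drug effect wanes in that week, a table labelled as end of double-blind treatment mixes on-drug and off-drug days in one arm and understates the effect. For the variables in 4.5.3.3.6, no visit label is given that would correct the reading.

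WRC also carries confirmatory weight. SAP 4.1.3.2 tests it fourth in the fixed sequence, and a failure there blocks MWT. The same section of the SAP equates the model's visit window with D49-D63, so two programmers could produce different WRC datasets and each cite the text. Unless one window is fixed first, the choice could be made after unblinding. Neither dataset would hold the two on-treatment weeks that the protocol names.

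**Working it through.** **Window lengths.** Nominal days from the schedule: V4 = D21, V5 = D28, V6 = D49, V7 = D56, V8 = D63. Each window is split at D56.

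| Window | Days | On treatment | Placebo week |
|---|---|---|---|
| DB2 by day label, D49-D63 | 63 − 49 = 14 | 7 | 7 (1/2) |
| DB2 by visit label, V6-V7 | 56 − 49 = 7 | 7 | 0 |
| DB4 by day label, D21-D63 | 63 − 21 = 42 | 35 | 7 (1/6) |
| DB4 by visit label, V4-V7 | 56 − 21 = 35 | 35 | 0 |
| Stable-dose phase, V5-V7 | 56 − 28 = 28 | 28 | 0 |
| Last two weeks before V7, D42-D56 | 56 − 42 = 14 | 14 | 0 |

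The SAP's stated lengths of 2 and 6 weeks reproduce from the day labels only. The visit labels in the same sentence give 1 and 5 weeks.

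**Denominator.** Under the visit-date rule in SAP 4.1.5.5, V6-V7 is 56 − 49 + 1 = 8 days. With ±2-day visit windows it runs from 54 − 51 + 1 = 4 to 58 − 47 + 1 = 12 days, so it never reaches 14.

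**Dilution.** The documents give no WRC effect size, attack rate or dispersion, so these are assumptions. Take an on-treatment rate ratio of 0.50. The washout-week ratio is 0.75 if half the reduction is lost and 1 if all of it is lost.

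- D49-D63: (0.5 + 0.75)/2 = 0.625 and (0.5 + 1)/2 = 0.75. The log effect shrinks by 32% and 58%.
- D21-D63: (5 × 0.5 + 0.75)/6 = 0.542 and (5 × 0.5 + 1)/6 = 0.583. The log effect shrinks by 12% and 22%.
- If the effect persisted in full through washout, both windows would still show 0.50.
- For true ratios from 0.4 to 0.8 with immediate full loss, D49-D63 would show 0.70 to 0.90.

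**Illustrative power.** Wald test on the log rate ratio, two-sided 0.05, with variance = (1/(μ0·w) + k)/n0 + (1/(μ0·RR·w) + k)/n1. Here μ0 is the placebo attack rate per week, w the weeks observed, and k the dispersion. The model is restricted to type 1 patients. The two cataplexy shares come from the Protocol Introduction (about 80%; of 36 + 72, taken as 29 and 57) and SAP section 3 (one third; 12 and 24).

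Worked case with μ0 = 5, k = 1, 29 vs 57:

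- Two on-treatment weeks: 1.1/29 + 1.2/57 = 0.0590, SE 0.243, 0.693/0.243 = 2.85, power 81%.
- One on-treatment week: 1.2/29 + 1.4/57 = 0.0659, SE 0.257, 0.693/0.257 = 2.70, power 77%.

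| Scenario | Two on-treatment weeks | One week (literal V6-V7) | D49-D63, half return | D49-D63, full return |
|---|---|---|---|---|
| 5/week, k = 1, 29 vs 57 | 81% | 77% | 49% | 22% |
| 5/week, k = 2, 29 vs 57 | 55% | 52% | 29% | 14% |
| 5/week, k = 1, 12 vs 24 | 45% | 41% | 24% | 12% |
| 2/week, k = 1, 29 vs 57 | 75% | 65% | 44% | 20% |

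**Baseline.** SAP 4.5.3.2.3 uses D-28 to D0, whereas Protocol 3.3.2 uses two weeks. Under Protocol 5.2.1, V0 at D-28 applies only to patients on prohibited or anticataplectic treatment. For patients who start at V1, D-28 to D-14 does not exist.

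**The case against.** The strongest reply is that the confirmatory test has one stated window. The model sentence says V6-V7 with no day label, and the visit-date rule in SAP 4.1.5.5 then leads to V6 and V7 with no placebo week. The D63 labels sit only in the descriptive bullets. On that reading the power cost is small, and WRC is fourth of five endpoints, so UNS, PDSS and UNS-CTP are untouched. This is correct, and it limits the concern: the large losses in the last two columns are hypothetical and need the model to be programmed as D49-D63. The SAP's own gloss permits that, so it cannot be ruled out.

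Several other points also stand. The visit labels come from the protocol, which attaches two weeks to visits one week apart and four weeks of stable dosing to a five-week span. Part of the fault therefore starts there. The SAP is loose elsewhere: 4.5.3.2.3 speaks of a 13-week double-blind phase, and 4.5.4.5 ends that phase at V8. The power formula is simpler than the planned model, which adjusts for baseline WRC and centre and uses a rate rounded to an integer. Dilution requires the effect to wane during washout, and the documents give no offset rate. The table shells, which might show the intended intervals, were not available.

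It can also be argued that deleting D63 would be enough. That removes the placebo week but leaves the model on about one week instead of two, with a length that varies by patient. Expressing WRC as a weekly rate, and letting the denominator shorten for patients who start at V1, keeps the rates computable. It does not give every patient the same window.

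**Conclusion.** The concern holds. The label contradiction, the placebo week inside the D63 windows and the absence of any two-week on-treatment window follow from the visit schedule alone and rest on no assumption.

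As written, the descriptive diary tables would contain half (DB2) or one sixth (DB4) placebo-week days. Read literally, the confirmatory test is free of the placebo week but covers 8 days nominal instead of two weeks. The larger power loss arises only if the test inherits D49-D63 and the effect wanes in washout. The power figures illustrate order of magnitude under an assumed rate ratio of 0.50 and assumed attack rates and dispersions.

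This should be fixed before unblinding. It does not bear on the primary endpoint.

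**What to change.** Before unblinding, amend SAP 4.5.3.2.3 and 4.5.3.3.6 so that one set of windows, all ending at V7, serves both the model and the tables:

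- **DB2:** the last 14 diary days before V7 (nominally from D42 up to V7 at D56), used in the negative binomial model.
- **DB4:** the stable-dose phase V5-V7 (D28-D56), with a note reconciling the protocol's V4 to V7 label.
- **Baseline:** the 14 diary days before V2, as in the protocol.
- **Washout:** D56-D63 reported separately.
- **Denominator in 4.1.5.5:** completed diary days instead of visit dates, because D42 is not a visit.

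The cost is a SAP clarification and a small amount of reprogramming at diary-day level. No new data are needed, because the diary is completed every evening from V0 to V8.
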